3.2. Study Oversight for Safety Evaluation

Early trial termination will be the result of the criteria specified below:

Quality or quantity of data recording is inaccurate or incomplete.

Poor adherence to protocol and regulatory requirements.

Incidence or severity of adverse drug reaction in this or other studies indicates a potential health hazard to subjects.

Plans to modify or discontinue the development of the study drug.

In the event of an AstraZeneca decision to no longer supply study drug, ample notification will be provided so that appropriate adjustments to subject treatment can be made.

4. Patient Selection, Enrollment, Restrictions, Discontinuation and Withdrawal

Each patient must meet all of the inclusion criteria and none of the exclusion criteria for this study. Under no circumstances will there be exceptions to this rule.

4.1. Inclusion Criteria

For inclusion in the study, patients should fulfill the following criteria:

18 Nov 2020 Page **59** of **164**

- 1. Written informed consent and any locally-required authorization (e.g., HIPAA in the USA, EU Data Privacy Directive in the EU) obtained from the subject prior to performing any protocol-related procedures, including screening evaluations
- 2. Age > 18 years at time of study entry or Adult male or female (according to age of majority as defined as ≥18 years).
- 3. Eastern Cooperative Oncology Group (ECOG) performance status of 0 or 1
- 4. Life expectancy of > 6 months
- 5. Body weight >30kg
- 6. Adequate normal organ and marrow function as defined below:
- 7. Haemoglobin ≥ 9.0 g/dL
- 8. Absolute neutrophil count (ANC) $\geq 1.5 \times 10^9/L$ (≥ 1500 per mm³)
- 9. Platelet count $\ge 100 \times 10^9 / L (\ge 100,000 \text{ per mm}^3)$
- 10. Serum bilirubin ≤ 1.5 x institutional upper limit of normal (ULN). <<This will not apply to subjects with confirmed Gilbert's syndrome (persistent or recurrent hyperbilirubinemia that is predominantly unconjugated in the absence of hemolysis or hepatic pathology), who will be allowed only in consultation with their physician.
- 11. AST (SGOT)/ALT (SGPT) ≤ 2.5 x institutional upper limit of normal unless liver metastases are present, in which case it must be ≤ 5x ULN
- 12. Serum creatinine CL>40 mL/min by the Cockcroft-Gault formula (Cockcroft and Gault 1976) or by 24-hour urine collection for determination of creatinine clearance:

Males:

Creatinine CL (mL/min) = $\frac{\text{Weight (kg) x (140 - Age)}}{\text{72 x serum creatinine (mg/dL)}}$

Females:

18 Nov 2020 Page **60** of **164**

Creatinine CL (mL/min) = Weight (kg) x
$$(140 - Age)$$
 x 0.85
72 x serum creatinine (mg/dL)

- 13. Subjects with a histologically-confirmed diagnosis of stage III non-small cell lung cancer.
- 14. Subjects with non-small cell lung cancer that has been deemed surgically resectable with lobectomy, by an attending thoracic surgeon.
- 15. Evidence of post-menopausal status or negative urinary or serum pregnancy test for female pre-menopausal subjects. Women will be considered post-menopausal if they have been amenorrheic for 12 months without an alternative medical cause. The following age-specific requirements apply:
 - Women <50 years of age would be considered post-menopausal if they have been amenorrheic for 12 months or more
 following cessation of exogenous hormonal treatments and if they have luteinizing hormone and follicle-stimulating
 hormone levels in the post-menopausal range for the institution or underwent surgical sterilization (bilateral oophorectomy
 or hysterectomy).
 - Women ≥50 years of age would be considered post-menopausal if they have been amenorrheic for 12 months or more
 following cessation of all exogenous hormonal treatments, had radiation-induced menopause with last menses >1 year ago,
 had chemotherapy-induced menopause with last menses >1 year ago, or underwent surgical sterilization (bilateral
 oophorectomy, bilateral salpingectomy or hysterectomy).
- 16. Subject is willing and able to comply with the protocol for the duration of the study including undergoing treatment and scheduled visits and examinations including follow up.

4.2. Exclusion Criteria

Subjects should not enter the study if any of the following exclusion criteria are fulfilled:

- 1. Involvement in the planning and/or conduct of the study (applies to both AstraZeneca staff and/or staff at the study site).
- 2. Participation in another clinical study with an investigational product during the last 4 weeks or the equivalent of 5 half-lives of the first dose of study treatment, whichever is shorter.

18 Nov 2020 Page **61** of **164**

- 3. Concurrent enrolment in another clinical study, unless it is an observational (non-interventional) clinical study or during the follow-up period of an interventional study.
- 4. Any previous treatment with a PD1 or PD-L1 agent including durvalumab or an CTLA-4 drug, including tremelimumab.
- 5. Any unresolved toxicity NCI CTCAE Grade ≥2 from previous anticancer therapy with the exception of alopecia, vitiligo, and the laboratory values defined in the inclusion criteria
- 6. Subjects with Grade ≥2 neuropathy will be evaluated on a case-by-case basis after consultation with the Study Physician.
- 7. Subjects with irreversible toxicity not reasonably expected to be exacerbated by treatment with durvalumab may be included only after consultation with the Study Physician.
- 8. Any concurrent chemotherapy, IP, biologic, or hormonal therapy for cancer treatment. Concurrent use of hormonal therapy for non-cancer-related conditions (e.g., hormone replacement therapy) is acceptable.
- 9. Radiotherapy treatment to more than 30% of the bone marrow or with a wide field of radiation within 4 weeks of the first dose of study drug.
- 10. Major surgical procedure (as defined by the Investigator) within 28 days prior to the first dose of IP. Note: Local surgery of isolated lesions for palliative intent is acceptable.
- 11. History of allogenic organ transplantation.
- 12. Active or prior documented autoimmune or inflammatory disorders (including inflammatory bowel disease [e.g., colitis or Crohn's disease], diverticulitis [with the exception of diverticulosis], systemic lupus erythematosus, Sarcoidosis syndrome, or Wegener syndrome [granulomatosis with polyangiitis, Graves' disease, rheumatoid arthritis, hypophysitis, uveitis, etc]). The following are exceptions to this criterion: Subjects with vitiligo or alopecia, Subjects with hypothyroidism (eg, following Hashimoto syndrome) stable on hormone replacement, Any chronic skin condition that does not require systemic therapy, Subjects without active disease in the last 5 years may be included but only after consultation with the study physician, Subjects with celiac disease controlled by diet alone.
- 13. Uncontrolled intercurrent illness, including but not limited to, ongoing or active infection, symptomatic congestive heart failure, uncontrolled hypertension, unstable angina pectoris, cardiac arrhythmia, interstitial lung disease, serious chronic gastrointestinal conditions associated with diarrhea, or psychiatric illness/social situations that would limit compliance with study requirement, substantially increase risk of incurring AEs or compromise the ability of the patient to give written informed consent

18 Nov 2020 Page **62** of **164**

- 14. History of another primary malignancy that requires active ongoing treatment or, in the opinion of the investigator, is likely to require treatment within 6 months of trial enrollment
- 15. History of active primary immunodeficiency
- 16. Active infection including tuberculosis (clinical evaluation that includes clinical history, physical examination and radiographic findings, and TB testing in line with local practice), hepatitis B (known positive HBV surface antigen (HBsAg) result), hepatitis C, or human immunodeficiency virus (positive HIV 1/2 antibodies). Subjects with a past or resolved HBV infection (defined as the presence of hepatitis B core antibody [anti-HBc] and absence of HBsAg) are eligible. Subjects positive for hepatitis C (HCV) antibody are eligible only if polymerase chain reaction is negative for HCV RNA.
- 17. Current or prior use of immunosuppressive medication within 14 days before the first dose of durvalumab or tremelimumab. The following are exceptions to this criterion: Intranasal, inhaled, topical steroids, or local steroid injections (e.g., intra articular injection). Systemic corticosteroids at physiologic doses not to exceed 10 mg/day of prednisone or its equivalent, Steroids as premedication for hypersensitivity reactions (e.g., CT scan premedication).
- 18. Receipt of live attenuated vaccine within 30 days prior to the first dose of IP. Note: Subjects, if enrolled, should not receive live vaccine whilst receiving IP and up to 30 days after the last dose of IP.
- 19. Known allergy or hypersensitivity to any of the study drugs or any of the study drug excipients.
- 20. Prior randomisation or treatment in a previous durvalumab and/or tremelimumab clinical study regardless of treatment arm assignment.
- 21. Has history of (non-infectious) pneumonitis that required steroids, evidence of interstitial lung disease or active, non-infectious pneumonitis.
- 22. Prior history of thoracic irradiation for any indication.
- 23. Subjects who are only deemed suitable for surgical management of stage III NSCLC with pneumonectomy, as determined by an attending thoracic surgeon.
- 24. Any condition that, in the opinion of the investigator, would interfere with evaluation of study treatment or interpretation of patient safety or study results

18 Nov 2020 Page **63** of **164**

- 25. Female patients who are pregnant or breastfeeding or male or female patients of reproductive potential who are not willing to employ or employing an effective method of birth control from screening to 180 days after the last dose of durvalumab + tremelimumab combination therapy or 100 days after the last dose of durvalumab monotherapy, whichever is the longer time period
- 26. Uncontrolled psychiatric illness/social situations that would limit compliance with study requirements or compromise the ability of the subject to give written consent
- 27. Procedures for withdrawal of incorrectly enrolled patients are presented in Section 4.3. If a patient withdraws from participation in the study, then his or her enrollment code cannot be reused. Withdrawn patients will not be replaced.

4.3. Withdrawal of Subjects from Study Treatment/On Study

If incorrectly enrolled, subjects should discontinue study treatment and enrollment. Subjects may withdraw consent at any time for any reason or be dropped from the trial at the discretion of the investigator should any untoward effect occur. In addition, a subject may be withdrawn by the investigator if enrollment into the trial is inappropriate, the trial plan is violated, or for administrative and/or other safety reasons.

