3.1.2. Determination of Eligibility

After eligibility is established, the study staff will register participants. The following are required to be submitted for successful registration:

Registration forms 🔛

Copy of subject consent 🔛

Copies of the following documents:

- Diagnostic pathology report(s) [SEP]
- PET/CT or CT scan report, MRI or CT brain with contrast report
- Laboratory reports including: [stp]

o Complete blood count (CBC) with differential (including absolute lymphocyte count) and direct platelet count.

18 Nov 2020 Page **55** of **164**

- o Chemistry: Albumin, SGOT (AST), SGPT (ALT), Bilirubin (direct and total), Calcium, Creatinine, Glucose, Total protein, Urea nitrogen, Uric Acid, Electrolytes (including sodium, potassium, chloride and bicarbonate).
- o Liver function tests (AST, ALT, Total bilirubin, alkaline phosphatase)
- o Urinalysis (routine)
- o Baseline thyroid immune safety assay: Thyroid Stimulating Hormone (TSH). Abnormal endocrine results should be followed up per standard of care, and may require an endocrine consult and additional testing.
- o Pulmonary function report
- o Other documents, if requested.

Study treatment cannot begin until the patient is registered. Subjects who sign a consent form, but do not initiate protocol treatment for any reason (e.g., subjects who are screen failures), will be replaced and will not count towards our accrual goal. Also patients who do not stay enrolled through the DLT period, will be replaced and not count towards our accrual goal.

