4.4. Permanent Discontinuation of Study Therapy

An individual subject will not receive any further investigational product if any of the following occur in the subject in question:

Withdrawal of consent or lost to follow-up

Adverse event that, in the opinion of the investigator or the sponsor, contraindicates further dosing

Subject is determined to have met one or more of the exclusion criteria for study participation at study entry and continuing investigational therapy might constitute a safety risk

Pregnancy or intent to become pregnant

Any AE that meets criteria for discontinuation as defined in Section 9.3.

- Serious Adverse event related to thoracic radiation, with the exception of toxicities that do not meet the criteria for discontinuation as defined in Section 9.3.
- Dose-limiting toxicity (See Section 6.3 for definition of DLT).
- Grade ≥ 3 infusion reaction

18 Nov 2020 Page **64** of **164**

- Subject noncompliance that, in the opinion of the investigator or sponsor, warrants withdrawal; e.g., refusal to adhere to scheduled visits
- Initiation of alternative anticancer therapy including another investigational agent
- Confirmation of PD and investigator determination that the subject is no longer benefiting from treatment with durvalumab
 + tremelimumab

Subjects who are permanently discontinued from further receipt of investigational product, regardless of the reason (withdrawal of consent, due to an AE, other), will be identified as having permanently discontinued treatment.

Subjects who are permanently discontinued from receiving investigational product will be followed for safety per Section 9.0 and Appendix 2 or 3, including the collection of any protocol-specified blood specimens, unless consent is withdrawn or the subject is lost to follow-up or enrolled I another clinical study. All subjects will be followed for survival. Subjects who decline to return to the site for evaluations will be offered follow-up by phone every 3 months as an alternative.

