4.6. Replacement of Subjects

If subject withdraws from the study, that subject will be replaced.

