6.3. Definition of Dose Limiting Toxicity (DLT)

Dose-limiting toxicities (DLTs) will be evaluated from the first day of administration of durvalumab (cohort 1) or durvalumab+tremelimumab (cohort 2), in this trial. The period for evaluating DLTs will be from the day of first administration of study therapy until 30 days after surgical resection or 100 days following the last dose of study therapy, whichever occurs later. Subjects who do not remain on the study up to this time for reasons other than DLT will be replaced with another subject. Grading of DLTs will follow the guidelines provided in the Common Terminology Criteria for Adverse Events (CTCAE) version 4.0. A patient who experiences a DLT will be permanently discontinued from treatment and will proceed to surgery after standard preoperative evaluation by a surgeon and anesthesiologist. Prior to surgery any treatment related toxicity should have resolved to ≤grade 1. [5]

A DLT will be defined as any Grade 3 or higher toxicity that occurs during the DLT evaluation period. Toxicity that is clearly and directly related to the primary disease or to another etiology is excluded from this definition. The following will be DLTs:

- Any Grade 4 irAE
- Any ≥ Grade 3 colitis
- Any Grade 3 or 4 non-infectious pneumonitis irrespective of duration
- Any Grade 2 pneumonitis that does not resolve to ≤ Grade 1 within 3 days of the initiation of maximal supportive care
- Any Grade 3 irAE, excluding colitis or pneumonitis, that does not downgrade to Grade 2 within 3
 days after onset of the event despite optimal medical management including systemic
 corticosteroids or does not downgrade to ≤ Grade 1 or baseline within 14 days
- Liver transaminase elevation > 8 × ULN or total bilirubin > 5 × ULN
- Any ≥ Grade 3 non-irAE, except for the exclusions listed below

The definition excludes the following conditions:

- Grade 3 fatigue lasting ≤ 7 days
- Grade 3 endocrine disorder (thyroid, pituitary, and/or adrenal insufficiency) that is managed
 with or without systemic corticosteroid therapy and/or hormone replacement therapy and the
 subject is asymptomatic
- Grade 3 inflammatory reaction attributed to a local antitumor response (e.g., inflammatory reaction at sites of metastatic disease, lymph nodes, etc.)
- Concurrent vitiligo or alopecia of any AE grade
- Grade 3 infusion-related reaction (first occurrence and in the absence of steroid prophylaxis) that resolves within 6 hours with appropriate clinical management

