12.1. Study Design

This is an open-label pilot study aimed at establishing the safety and feasibility of neoadjuvant immunoradiation prior to surgical resection of stage III NSCLC, that is deemed surgically resectable by a thoracic surgeon with lobectomy. Thoracic RT will be given at standard doses and fractionation to a total dose of 45Gy in 25 fractions, as per published phase III data⁴⁹, and using standard methods. In cohort 1, the safety and feasibility of durvalumab with concurrent thoracic RT, will be assessed. In this cohort, durvalumab will be administered at the standard dose of 1500mg IV every 4 weeks for 3 doses, as per ongoing phase III studies. If preliminary safety is established in cohort 1, the study will expand to include cohort 2, which will test the safety and feasibility of durvalumab plus tremelimumab with concurrent thoracic RT. In this cohort, durvalumab will be administered at the standard dose of 1500mg IV every 4 weeks for 3 doses, and tremelimumab will be administered at the standard dose of 75mg every 4 weeks for 3 doses. The primary endpoints of this study are safety and feasibility in cohort 1 and cohort 2 (if applicable). Patients will be observed for perioperative grade 3-4 adverse events through day 90 following the last dose of immunotherapy or until 30 days post-surgery, whichever is longer. Safety and feasibility will be monitored continuously throughout the study through weekly meetings with investigators, as well as the planned Bayesian monitoring rules (see below). A set of markers of immune reactivity measured in lung tumor resection specimens, draining lymph nodes, and peripheral blood will be evaluated. Feasibility will be evaluated as the proportion of evaluable patients who successfully complete preoperative treatment and proceed to surgery without any extended treatment related delays. Extended treatment-related delay will be defined as >8 weeks from the day of completion of thoracic RT. For each cohort, we aim to accrue 16 evaluable patients, defined as those who receive at least one dose of durvalumab or durvalumab/tremelimumab administration and have complete toxicity follow-up. We plan to accrue 20 patients to ensure 16 evaluable patients are available for analysis. If less than 16 evaluable patients are available after accruing 20 patients, we will amend the protocol to ensure at least 16 evaluable patients are available for analysis.

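### Section 4.3 lets a patient be dropped from the trial for any untoward effect; with the replacement and evaluability rules, a toxicity that is not yet a DLT can leave the set used by the safety stopping rule

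*Combined protocol and SAP*

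**What the plan says.** **Leaving the trial.** Section 4.3 allows a patient to "be dropped from the trial at the discretion of the investigator should any untoward effect occur". It sets no grade, asks for no check against the DLT criteria, and does not mention continued follow-up.

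**Replacement and counting.**
- Section 3.1.2: "Also patients who do not stay enrolled through the DLT period, will be replaced and not count towards our accrual goal". It makes no exception for toxicity.
- Section 6.3: "Subjects who do not remain on the study up to this time for reasons other than DLT will be replaced with another subject".
- Section 4.6: "If subject withdraws from the study, that subject will be replaced".
- Section 4.2, item 27: "Withdrawn patients will not be replaced".
- Section 12.1 limits evaluable patients to those "defined as those who receive at least one dose of durvalumab or durvalumab/tremelimumab administration and have complete toxicity follow-up". It plans 20 accrued per cohort to obtain 16 evaluable.

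**Follow-up.**
- Section 4.4: "Subjects who are permanently discontinued from receiving investigational product will be followed for safety per Section 9.0". Its exceptions are withdrawn consent, loss to follow-up and entry to another study.
- Section 3.1.6.2 requires weekly record review from the start of therapy to the later of 100 days after the last dose or 30 days after surgery. This is the DLT window of Section 6.3.
- Section 8.1.3 sends early discontinuers to the safety visit and then to follow-up.
- Section 9.3.1 records adverse events through follow-up.

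**The concern.** Safety is a co-primary endpoint, and Section 12.2.2 monitors it from the third evaluable patient in a cohort of 16 evaluable patients. If a patient can be taken off study because of a toxicity that has not yet met a DLT definition, and then be replaced, removal depends on the outcome being measured. The replacement starts with no toxicity, so the counted DLT proportion tends to be too low and the stopping rule less likely to act. The same counts inform whether cohort 2 opens.

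Such patients can exist. Some Section 6.3 criteria depend on time: grade 2 pneumonitis counts only if it has not settled within 3 days of maximal supportive care, and grade 3 immune-related events other than colitis and pneumonitis are judged at 3 and 14 days. The window is also long, so a patient dropped for a lower-grade event might have gone on to a DLT later in it.

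**Working it through.** **1. The path through the text.** A patient has an untoward effect that is not a DLT. Section 4.3 permits a drop from the trial. The patient is then no longer enrolled (3.1.2: replaced, not counted), has left for a reason other than DLT (6.3: replaced), and may lack complete toxicity follow-up (12.1: not evaluable). Sections 3.1.6.2, 4.4, 8.1.3 and 9.3.1 imply that follow-up continues, and 4.2 item 27 denies replacement. No sentence says which prevails.

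**2. Reproducing the plan's rule.** Inputs from Section 12.2.2: prior Beta(0.05, 0.95); suspend if P(rate > 25%) is at least 70%; monitoring from n = 3 to 16. With x DLTs in n patients the posterior is Beta(0.05 + x, 0.95 + n − x). The smallest x that triggers a stop is 2 at n = 3–4, 3 at 5–7, 4 at 8–11, 5 at 12–14 and 6 at 15–16. An exact forward recursion with these boundaries gives:

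| True DLT rate | Table 10.2, stops | Exact |
|---|---|---|
| 0.15 | 15.8% | 16.3% |
| 0.20 | 29.3% | 29.3% |
| 0.25 | 43.1% | 44.3% |
| 0.30 | 60% | 59.4% |
| 0.35 | 72.8% | 72.8% |

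The largest gap is 1.2 points, so the rule is reproduced.

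**3. Sensitivity to one patient (no drop rate needed).** Posterior probability that the rate exceeds 25%:
- 2/3 gives 0.857 (stop); 1/3 gives 0.448 (continue).
- 3/6 gives 0.841 (stop); 2/6 gives 0.552 (continue).
- 6/16 gives 0.818 (stop); 5/16 gives 0.641 (continue).

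The reported exact 95% interval would move from 15.2%–64.6% (6/16) to 11.0%–58.7% (5/16).

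**4. Illustration with an assumed drop share.** Let p be the true DLT rate and d the share of would-be DLT patients dropped first and replaced. The documents give no value for d. If nobody else is dropped, the counted rate is q = p(1 − d)/(1 − pd). For p = 0.30 and d = 20%, q = 0.24/0.94 = 25.5%.

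| p | d | Counted rate q | Stops |
|---|---|---|---|
| 0.30 | 0 | 30.0% | 59.4% |
| 0.30 | 10% | 27.8% | 53.0% |
| 0.30 | 20% | 25.5% | 46.0% |
| 0.30 | 50% | 17.6% | 22.8% |
| 0.25 | 0 | 25.0% | 44.3% |
| 0.25 | 20% | 21.1% | 32.3% |

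For scale: at p = 0.30 and d = 20%, filling 16 counted places means dropping on average 16 × 0.06/0.94 = 1.0 patient. That is within the 20 − 16 = 4 non-evaluable patients Section 12.1 allows per cohort before an amendment.

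**5. If other patients are dropped too.** With share e of non-DLT patients also dropped, q = p(1 − d)/[p(1 − d) + (1 − p)(1 − e)]. For p = 0.30 and d = 20%, e = 10% gives 0.24/(0.24 + 0.63) = 27.6%, and e = 20% gives 0.24/(0.24 + 0.56) = 30%, which is no bias.

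**The case against.** The strongest reply is that the plan already keeps these patients under observation. Section 4.4 does not list an investigator's drop among its exceptions, Section 3.1.6.2 reviews records over the whole DLT window even for patients whose care moves elsewhere, and Section 9.3.1 follows serious events beyond study participation. The primary safety endpoint in Section 12.2.1 carries no evaluable-only restriction, the synopsis speaks of all treated patients, and Table 10.1 is headed by patients treated. Section 6.3 does not replace a patient who leaves because of a DLT. The time-dependent DLT criteria mostly run for days, and grade 3–4 pneumonitis, grade 3 or higher colitis and grade 4 immune-related events count at once.

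Much of this stands, and it rules out two stronger readings. A reader might infer that the plan removes patients with toxicity from the safety data. It does not: recorded events remain recorded, established DLTs are protected by Section 6.3, and follow-up is called for in four places. A reader might also infer that these patients leave the recurrence-free survival analysis. Nothing in Sections 10.2.4 or 12.3.2 supports that: RFS runs from the start of therapy by Kaplan-Meier with no evaluable restriction.

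The reply does not settle which patients the stopping rule counts. Even with follow-up continuing, Section 3.1.2 still does not count a patient who is no longer enrolled, and Section 12.2.2 monitors evaluable patients. Item 27 of Section 4.2 does not close the gap, because Sections 3.1.2 and 4.6 say the opposite.

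**Conclusion.** The concern holds as a conflict between sections that leaves room for outcome-dependent removal from the evaluable set. On one reading that the text allows, a patient with a toxicity short of a DLT can be dropped, left uncounted and replaced, and the DLT proportion can be biased downward. On another, the patient stays in follow-up and is not replaced. The plan does not choose.

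The effect on the stopping rule cannot be estimated from the documents. The fall from 59.4% to 53.0% or 46.0% at a true rate of 30% is a one-sided illustration. It assumes a 10% or 20% drop share with no source in the plan, that only would-be DLT patients are dropped, and that their toxicity is not counted. It shrinks, and can vanish, if patients without a DLT are dropped as well. What needs no assumed drop share is that one uncounted DLT can reverse a decision at n = 3, 6 or 16.

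**What to change.** - **Section 4.3:** separate stopping study treatment from leaving the study. An untoward effect should be a ground for the first only, with on-study safety, surgery and survival follow-up continuing as in Section 4.4 unless consent is withdrawn. The clinical decision to stop treatment is not at issue and stays with the investigator.
- **Sections 3.1.2, 6.3 and 12.1:** state that a dosed patient who stops because of any adverse event stays in the safety numerator and denominator, and that a replacement only adds a patient.
- **Sections 4.2 item 27 and 4.6:** reconcile the two opposite statements on replacing withdrawn patients.
- **Table 10.1:** if replacements add to the count, extend the boundaries beyond n = 16 with the same prior and threshold.

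The cost is one protocol amendment with short wording changes in six sections (3.1.2, 4.2, 4.3, 4.6, 6.3, 12.1) and a longer boundary table. No new visits are needed, since Sections 3.1.6.2 and 4.4 already require the follow-up. Sections 6.2.2.5, 6.2.3.1 and 6.2.3.3 already provide a model: they replace certain patients while keeping them in safety follow-up.
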